7.4.3 Human Genotyping

SNP genotype is considered missing if either allele is not A, C, G, T, DEL or INS.

7.4.4 Laboratory Test Results

Toxicity grades are based on standard values, standard lower limit of normal (LLN), and standard ULN, as applicable. If a laboratory value that is graded as a multiple of the ULN or LLN falls between 2 toxicity grades, then the higher toxicity grade is assigned (e.g., an ALT value that is 2.53 x ULN is classified as Grade 2, not Grade 1).

7.4.5 Non-Study Medications

Non-study medications are coded using the BMS WHO dictionary. Missing and partial non-study medication start and stop dates (including unknown and continuing) are imputed according to the Non-Study Medication Domain Requirements Specifications in place at the start of

programming.¹¹ Imputed dates are used to classify medications as previous, current, concomitant or post-treatment.

7.4.6 Viral Genotyping and Phenotyping

If there are multiple records on the same collection day, then the last record assayed is selected. Only records from the central laboratory are used.

7.4.7 Virology

The central laboratory uses the Roche COBAS® AmpliPrep/COBAS® TaqMan® HCV Test v2.0 to measure HCV RNA level. This assay has limit of detection = 15 IU/mL, LLOQ = 15 IU/mL, and upper limit of quantification (ULOQ) = 1.0×10^8 IU/mL.

HCV RNA viral loads are reported by the central laboratory and listed as follows:

- (1) Actual numeric values for detectable virus within LLOQ and ULOQ;
- (2) "> ULOO" for detectable virus above ULOO;
- (3) "< LLOQ, HCV RNA detected" for detectable virus below LLOQ;
- (4) "No HCV RNA detected" for undetectable virus.

Analyses of HCV RNA < LLOQ TND use data corresponding to item 4 above. Analyses of HCV RNA < LLOQ TD or TND use data corresponding to items 3 and 4 above.

For analyses of HCV RNA as a continuous parameter, HCV RNA values in the original scale of IU/mL are imputed with a value of 1 more (or 1 less) if an inequality ">" ("<") is present (items 2 and 3 above), and a value of LLOQ - 1 if undetectable (item 4 above). These values are then transformed to the log₁₀ scale.

If there are multiple values on the same collection day, then the first value assayed is selected.

Only records from the central laboratory are used.

8 CONTENT OF REPORTS

The timing of interim analyses will depend on the availability of Day 10 PK results. An interim analysis will be performed when the first 5 participants in each age cohort complete the Day 10 PK sample collection.

If the median plasma exposure in a cohort is outside the predefined therapeutic range, then dose modification will be performed using pediatric formulations of DCV, and an additional 5 participants will be enrolled. Another interim analysis will be performed when these additional participants complete the Day 10 PK sample collection in order to confirm the exposure at the modified dose. All Day 10 PK interim analyses will focus on PK and select safety listings (e.g., AEs, laboratory tests, end of treatment subject status). In each cohort, enrollment will continue in order to achieve at least 8 evaluable participants per cohort.

Additional interim analyses will be performed when all participants in an age cohort complete the Follow-up Week 12 visit and when all participants complete the Follow-up Week 12 visit in order

to assess the primary and secondary endpoints. All endpoints except PK and durability of virologic response will be assessed.

The final analysis will be conducted when all participants complete long-term follow-up to assess long-term efficacy endpoints (durability of virologic response, and virologic resistance) and follow-up safety endpoints.

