
 To evaluate genotypic substitution(s) associated with virologic failure To assess the acceptability and palatability for the age-appropriate chewable tablet formulation, and acceptability for adult film-coated tablet 	
 Frequencies of NS5A and NS5B resistance-associated variants (RAVs) emergent at the time of virologic failure on treatment and during follow-up in non-responders Summary of responses from questionnaire assessing acceptability and palatability at Day 1, Week 4, and Week 12

[REDACTED]
	
[REDACTED]

[REDACTED]
	
[REDACTED]

Overall Design:

The study will be an open-label, single-arm, descending-age cohort trial evaluating the PK profile, safety, tolerability, and efficacy of DCV+SOF administered for 12 weeks to paediatric participants (3 < 18 years of age) with CHC virus infection.

Enrolment will begin with Cohort 1, followed by Cohorts 2 and 3.

- Cohort 1: 12 to < 18 years of age
- Cohort 2: 6 to < 12 years of age
- Cohort 3: 3 to < 6 years of age

Note: Due to the early termination of the study, only participants 12 to <18 years of age were enrolled in the study into Cohort 1; no participants will be enrolled in Cohorts 2 and 3.

Samples for assessment of DCV PK will be collected on Day 10 of the study. In each cohort, DCV PK will be evaluated after the initial 5 participants complete their Day 10 visit in order to determine if the target DCV exposure is achieved.

Enrolment in Cohorts 2 and 3 will be dependent on the availability of the European Commission (EC) approved SOF age appropriate dose and formulation for the corresponding age cohort.

Post treatment, participants will be followed for 12 weeks to assess sustained virologic response at Post-treatment Week 12 (SVR12) and then for an additional 2 years (96 weeks) as long-term follow-up to assess [REDACTED], durability of response, long-term safety, and the persistence of resistance variants in non-responders.

Note: With the early termination of this study, participants will not complete the initially planned 96 weeks of LTFU. As of 18 October 2019, all participants will have completed their Post Treatment Week 24 visit and approximately 41 to 53 weeks of post-treatment follow-up;

participants will be asked to return to the study site to perform an EOS visit upon approval of the revised protocol.

Number of Participants:

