10 STATISTICAL CONSIDERATIONS

10.1 Sample Size Determination

Note: Not Applicable due to the early termination of the study; a total of 5 participants will have been enrolled in the study into Cohort 1.

A minimum of 30 participants, assigned to 3 age descending cohorts, will be evaluated for the primary endpoint (PK) with at least 8 participants assessed in each age cohort.

The primary objective of this study is to evaluate the PK of DCV. The PK profile of DCV has been well characterized in the clinical development program and it has been noted that DCV is associated with predictable pharmacokinetics. The intra-participant variability for DCV C_{max} and AUC (INF) was assessed from clinical studies where single oral doses of DCV were administered with or without food and were estimated to be low with a % CV of 18% for C_{max} and 10% for AUC (INF). Similarly, the inter-participant variability in DCV C_{max} and AUC were assessed from clinical studies where single and multiple oral doses of DCV administered alone, and with or without food in some cases, was identified to be modest with % CV values of 37.5% for C_{max}

and 35% for AUC. PK will be assessed in all participants, however, due to the low observed variability in DCV exposure, assessment of the PK in the initial 5 participants per age cohort will provide the necessary information to match DCV exposures between adults and paediatric participants and either allow enrolment to be initiated in the next descending age cohort(s) or indicate that additional participants need to be enrolled in the cohort with a modified dose. Enrolment will continue in each cohort, after the initial 5 participants have completed their Day 10 assessments, to have a minimum of 8 evaluable participants in each cohort.

Descriptive summary statistics will be provided for the secondary endpoints in this study.

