10.3.4 Pharmacokinetic Analyses

Individual pharmacokinetic parameter values for DCV will be derived from plasma concentration versus time using non-compartmental methods or model based approaches as needed on Day 10 (± 3 days). Values will be summarized with descriptive statistics (n, arithmetic mean, standard deviation, geometric mean, coefficient of variation, median, minimum, maximum) by age cohort. Parameters will include: Cmin, Cmax, Tmax, AUC (TAU), and CLT/F.

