10.3.6 Interim Analyses

The timing of interim analyses will depend on the availability of Day 10 PK results. An interim analysis will be performed when the first 5 participants in each age cohort complete the Day 10 PK sample collection.

If the median plasma exposure in a cohort is outside the predefined therapeutic range, then dose modification will be performed using paediatric formulations of DCV, and an additional 5 participants will be enrolled. Another interim analysis will be performed when these additional participants complete the Day 10 PK sample collection in order to confirm the exposure at the modified dose. All Day 10 PK interim analyses will focus on PK and select safety listings (eg, AEs, laboratory abnormalities, participant disposition). In each cohort, enrollment will continue in order to achieve at least 8 evaluable participants per cohort.

Additional interim analyses will be performed when all participants in an age cohort complete the Post-Treatment Week 12 visit and when all participants complete the follow-up Week 12 visit in order to assess the primary and secondary endpoints.

The final analysis will be conducted when all participants complete long-term follow-up to assess long-term efficacy (██████████), safety, and evolution of resistance variants in virologic failures.

The Statistical Analysis Plan will further describe the planned interim analyses.

Note: An interim analysis will not be performed. As only 5 subjects will be enrolled in this study, analyses are not needed to guide dosing for additional participants.

- [REDACTED]
- [REDACTED]
- [REDACTED]
- [REDACTED]
- [REDACTED]
- [REDACTED]
- [REDACTED]
- [REDACTED]
- [REDACTED]
- [REDACTED]
- [REDACTED]

- [REDACTED]
- [REDACTED]
- [REDACTED]
- [REDACTED]

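### Does SAP section 8 leave the primary PK endpoint without a report, or without its exposure comparison, now that the interim analyses are cancelled?

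*SAP*

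**What the plan says.** **Reporting schedule.** SAP 8 sets out three layers.
- Day 10 PK interims run after the first 5 participants in each cohort. The rule "If the median plasma exposure in a cohort is outside the predefined therapeutic range" opens the path to a modified dose and 5 more participants.
- Additional interims run at Follow-up Week 12, with the purpose and exclusion "to assess the primary and secondary endpoints. All endpoints except PK and durability of virologic response will be assessed".
- Last comes this: "The final analysis will be conducted when all participants complete long-term follow-up to assess long-term efficacy endpoints (durability of virologic response, and virologic resistance", together with follow-up safety.

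Protocol 10.3.6 describes the same Week 12 analyses, "when all participants complete the follow-up Week 12 visit in order to assess the primary and secondary endpoints", with no PK exclusion.

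**Early termination.** A note in Protocol 10.3.6 says no interim will be performed and gives the reason: "As only 5 subjects will be enrolled in this study, analyses are not needed to guide dosing for additional participants". The note in Protocol 10.3 repeats the cancellation. It keeps PK, SVR and selected safety for the adolescents, drops resistance and palatability, and rules out statistical analyses because so few were enrolled. Protocol 4 withdraws durability.

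**PK outputs.** Protocol 10.3.4 states: "Values will be summarized with descriptive statistics (n, arithmetic mean, standard deviation, geometric mean, coefficient of variation, median, minimum, maximum) by age cohort". SAP 6.7 specifies the matching concentration, parameter and trough summaries, plots and listings.

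**Target exposure.** The synopsis has PK evaluated after the first 5 participants per cohort "in order to determine if the target DCV exposure is achieved". Protocol 10.1 says those 5 will "provide the necessary information to match DCV exposures between adults and paediatric participants", but that section now opens with a note marking it not applicable.

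**The concern.** Read alone, SAP 8 reports PK only in the Day 10 interims. The Week 12 analyses exclude it and the final analysis does not list it. With the interims cancelled, SAP 8 names no surviving report for the study's sole primary endpoint.

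The check of median exposure against its target range appears, in the visible text, only with the first-5 evaluation and its repeat after a dose change. It is not in Protocol 10.3.4 or SAP 6.7. Exactly 5 participants were enrolled, so one could argue the planned check is still possible and has dropped out without a decision.

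Finally, the bar on statistical analyses in Protocol 10.3 stands beside unannotated descriptive PK statistics (10.3.4) and an exact 95% confidence interval for SVR12 (10.3.1, SAP 6.5.1.1). At stake would be an unreported primary endpoint, an unstated exposure conclusion, and an SVR12 percentage from 5 participants shown without its uncertainty.

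**Working it through.** The documents give no figure to reproduce here, so the first step is to follow each item through them.

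| Item | SAP 8 | Revised protocol | Output defined in |
|---|---|---|---|
| PK | Day 10 interims only | Reported (10.3 note) | Protocol 10.3.4; SAP 6.7 |
| SVR12 | Week 12 interims | Reported (10.3 note) | Protocol 10.3.1; SAP 6.5.1.1 |
| Safety | Interims and final | Selected items reported (10.3 note) | Protocol 10.3.3; SAP 6.6 |
| Resistance | Final | Withdrawn (10.3, 10.3.2) | not needed |
| Durability | Final | Withdrawn (4) | not needed |

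**Does PK have a report?** Yes, through the 10.3 note. SVR12 is in the same position: SAP 8 places it only in interims, and the protocol note keeps it. Of the three final-analysis items in SAP 8, two (durability and resistance) are withdrawn and one (follow-up safety) remains. Under the planned design, the interims would have covered 3 × 5 = 15 of at least 30 participants, leaving later participants' PK with no named report. With 5 enrolled, that gap no longer exists.

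**Is the range comparison part of the endpoint?** Protocol Table 4-1 and SAP Table 3-1 define the endpoint as the Day 10 parameters. Neither includes a range. In Protocol 10.3.6 and SAP 8 the range only decides whether dose and enrolment change, and the cancelling note gives the end of that purpose as its reason.

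**What would the comparison add?** The median, minimum and maximum are already reported.
- The minimum-to-maximum interval covers the true median with probability 1 − 2 × 0.5^5 = 93.75% if all 5 have evaluable Day 10 PK, and 1 − 2 × 0.5^4 = 87.5% if 4 do.
- With the stated between-participant CV of 35% for AUC, the log-scale SD is √ln(1 + 0.35²) = 0.340. The 95% interval for a geometric mean at n = 5 is exp(±2.776 × 0.340/√5), or 0.66 to 1.53 times the estimate.
- The range is not visible. Assuming log-normal AUC with its true median at the range's centre, the chance that the median of 5 falls outside is 22% for an assumed range of 0.80–1.25, 5.0% for 0.70–1.43 and 0.02% for 0.50–2.00.

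An in-or-out statement would therefore be feasible but imprecise, and would depend heavily on the range.

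**What hangs on the SVR12 interval?** Exact (Clopper-Pearson) 95% limits:
- 5/5: lower limit 0.025^(1/5) = 0.478, so 47.8% to 100%.
- 4/4: lower limit 0.025^(1/4) = 0.398, so 39.8% to 100%.
- 4/5: the lower limit solves 5p⁴(1 − p) + p⁵ = 0.025, giving 0.284; the upper limit is 0.975^(1/5) = 0.995; so 28.4% to 99.5%.

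The principal method carries the next value backwards. The synopsis says all participants completed Post-Treatment Week 24, a visit with scheduled HCV RNA, and Protocol 10.3.2 reports no virologic failure. One missing Week 12 value would thus be expected to give 5/5 under the principal method, 4/4 under observed values, and 4/5 only under the mITT sensitivity method.

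**The case for a change.** The strongest case for acting is that the text is inconsistent and cheap to repair. Other withdrawn items carry their own notes (Protocol 10.3.2, 10.3.5.1 and 10.3.6), while 10.3.1 and 10.3.4 carry none, so a programmer must infer what the bar on statistical analyses covers. The synopsis sentence about determining whether target exposure is achieved is not labelled an interim and has no cancelling note of its own. A reader of the PK report may well want to know whether these adolescents reached the intended exposure.

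Part of this stands. SAP 8 is out of step with the revised protocol, and the status of the SVR12 interval is not stated. The remainder is weaker. The mismatch is a version lag across the whole SAP, which still describes three cohorts and at least 30 participants; its date is not visible, so it may predate the revision. The same protocol note that bars statistical analyses commits PK and SVR to be reported, so it cannot sensibly bar descriptive summaries. The natural reading is that no inferential testing is done. The synopsis sentence describes the same first-5 evaluation, whose dosing purpose has ended. Some design text is blacked out, so it cannot be said that no other comparison was planned.

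**Conclusion.** No change is needed. The clash over PK lies in analyses that will not take place, and the protocol states what is reported in their stead, with outputs already specified. The leftover durability, resistance and interim text is a failure to update, and the protocol notes resolve it. Leaving out the range comparison drops a dose-adjustment trigger that no longer has a use. Anyone holding the range can set the reported median, minimum and maximum beside it.

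The only open choice is whether SVR12 is printed with its exact interval. The section-level text specifies one, and an analyst would sensibly keep it. If it were omitted, the reader could recover 47.8% to 100% from a count of 5/5. No rule here would produce a wrong result, and no data are lost.

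This rests on three points: the Protocol 10.3 note governs reporting; HCV RNA is available at Week 24 for anyone missing Week 12; and PK summaries use whichever of the 5 have evaluable Day 10 data, a number the documents do not give.

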APPENDIX 1 RELEVANT PROTOCOL DEVIATIONS

Relevant protocol deviations are summarized as categorical parameters for treated participants.

Eligibility Deviations

Eligibility deviations are based on those occurring during the pre-treatment period for the following categories:

- Inclusion criterion 2a: HCV genotype other than GT-1 to GT-6, including mixtures, during screening;
- Inclusion criterion 2b: HCV RNA < 1,000 IU/mL during screening;
- Inclusion criterion 2e: Presence of cirrhosis as defined in protocol.
 - A participant is considered to be non-cirrhotic if any one of the following criteria is met:
 - ◆ Liver biopsy results with F0-F3 stage of fibrosis by Metavir within 3 years before screening. Determined from the Fibrosis Staging CRF;
 - ♦ Fibroscan measurement < 12.5 kPa within 1 year before Day 1. Determined from the Fibrosis Staging CRF;
 - \bullet APRI \leq 0.5 during screening. Determined from the laboratory test.
 - A participant is considered to be cirrhotic if any one of the following criteria is met:
 - ♦ Liver biopsy results with F4 stage of fibrosis by Metavir at any time before screening. Determined from the Fibrosis Staging CRF;
 - ◆ Fibroscan measurement ≥ 12.5 kPa within 1 year before Day 1. Determined from the Fibrosis Staging CRF;
 - ♦ APRI > 0.5 during screening. Determined from the laboratory test.

If fibrosis stage data are available from several sources, then the liver biopsy supersedes Fibroscan, and Fibroscan supersedes APRI.

- Inclusion criterion 2f: Baseline weight < 10 kg;
- Inclusion criterion 3a: Age < 3 or > 18 years at enrollment;
- Exclusion criterion 1a: Positive serological test for HBV or HIV infection during screening. Defined as positive HBsAg, HIV-1 antibody, or HIV-2 antibody.
- Exclusion criterion 1e: Pre-treatment HCC. Identified from general medical history specify details (#) or fibrosis staging finding;
- Exclusion criterion 1i: Confirmed HbA1c ≥ 0.085 or $\geq 8.5\%$ during screening. Confirmed is defined as at least 2 consecutive measurements;
- Exclusion criterion 2a: Use of prohibited prior non-study medication (#). Defined as any of the following:
 - Any HCV NS5A inhibitor or SOF;
 - Any approved anti-HCV therapy < 12 weeks before Day 1;

Generic drug names are presented alphabetically as subcategories.

• Exclusion criteria 3b to 3i: Laboratory test findings during screening, with the following subcategories:

- Exclusion criterion 3b: ALT or AST > 10 x ULN
- Exclusion criterion 3c: Albumin < 35 g/L or < 3.5 g/dL
- Exclusion criterion 3d: Total bilirubin > 19 μmol/L or > 1.1 mg/dL without history of Gilbert syndrome. Gilbert syndrome is identified from general medical history specify details (#);
- Exclusion criterion 3e: Alpha fetoprotein > 50 ng/mL or > 50 µg/L
- Exclusion criterion 3f: ANC $< 1.5 \times 10^9$ cells/L or $< 1.5 \times 10^3$ cells/ μ L
- Exclusion criterion 3g: Hemoglobin < 100 g/L or < 10 g/dL
- Exclusion criterion 3h: Platelets < 100 x 10⁹ cells/L
- Exclusion criterion 3i: Creatinine clearance < 1 mL/s/m² or < 60 mL/min/1.73m², using the Schwartz formula.
- (#) Non-study medications and medical conditions marked above with # are identified by a BMS physician prior to database lock.

The screening portion of the pre-treatment analysis period begins at informed consent and ends before the start of study therapy (Day 1).

[figure not shown]
A participant with multiple pre-treatment measurements (e.g., HCV RNA) is considered to have an eligibility deviation only if all pre-treatment measurements meet the deviation criterion.

Participant Management Deviations

Participant management deviations are evaluated during the on-treatment or follow-up analysis period for the following categories:

- At least 2 consecutive missed doses of DCV before Day 10 PK sampling, or at least 1 missed dose of DCV within 2 days before Day 10 PK sampling. Missed doses of DCV are identified from interruptions or gaps between dosing records;
- At least twice of DCV target daily dose taken within 2 days before Day 10 PK sampling;
- DCV or SOF average daily dose < 80% of target daily dose;
- DCV or SOF interruption > 7 consecutive days;
- Continuation of study therapy after having virologic breakthrough;
- Use of prohibited non-study concomitant medication for more than 1 day, including anti-HCV medications (#). Generic drug names are presented alphabetically as subcategories;
- Use of non-study anti-HCV medication during follow-up (#). Generic drug names are presented alphabetically as subcategories;
- (#) Non-study medications marked above with # are identified by a BMS physician prior to database lock.

Anti-HCV Medications

Currently, the following non-study generic drugs are approved for HCV treatment: BROCE/INTAB/RIBAV, BOCEPREVIR, BROCE/INTA/RIBAV, DACLATASVIR*, DASABUVIR, DASAB/OMBIT/PARIT/RIBAV/RITON*, DASAB/OMBIT/PARIT/RITON*, ELBASVIR*, ELBVIR/GRAZO*, GLECAPREVIR, GLECA/PIBRE, GRAZOPREVIR, INTERFERON, INTERFERON ALFA, INTERFERON ALFA 1B, INTERFERON ALFA 2A, INTERFERON ALFA 2B, INTERFERON ALFA N1, INTERFERON ALFA N3, INTERFERON ALFACON, INTERFERON ALFACON 1, INTERFERON BETA, INTERFERON BETA 1A, INTERFERON BETA 1B, INTERFERON GAMMA, INTERFERON GAMMA 1B, INTA/RIBAV, INTA/RIBAV/TELAP, INTAA/RIBAV, INTAB/RIBAV, INTFER/RIBAV, LEDIP/RIBAV/SOFO*, LEDIPASVIR*, LEDIP/SOFO*, OMBITASVIR*, OMBIT/PARIT/RITON*, PARITAPREVIR, PIBRENTASVIR*, RIBAVIRIN, RIBAV/SOFO, SIMEPREVIR, SIMPRE/SOFO, SOFOSBUVIR, SOFO/VELPAT*, SOFO/VELPAT/VOXILA*, TELAPREVIR, VELPATASVIR*. The drugs asterisked ("*") are or contain NS5A inhibitors.

Other non-study medications that may be considered to have anti-HCV activity (depending on the reported name) are the following generic drug names: INVESTIGATIONAL ANTIVIRAL, INVESTIGATIONAL IMMUNOMODULATING AGENT, IMMUNOMODULATING AGENT.

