 - i) Documented liver biopsy results within 3 years before Screening suggestive of absence of cirrhosis (F0-F3 stage of fibrosis by METAVIR or equivalent)OR
 - ii) Documented Fibroscan (transient elastography) measurement within 1 year before Day 1 consistent with absence of cirrhosis (< 12.5 kPa)OR
 - iii) APRI score at Screening (aspartate aminotransferase to platelet ratio index) consistent with absence of liver cirrhosis (≤ 0.5).
If fibrosis stage data are available by several modalities, then the biopsy takes precedence over Fibroscan results, and Fibroscan measurements supersede APRI test.
- f) Participants with body weight ≥ 10 kg at Day 1; participants in Cohort 1 must have a body weight ≥ 45 kg at Day 1.

3) Age and Reproductive Status

- a) Males and Females, ages, 3 to < 18 years of age on Day 1 of study treatment.
- b) Females of childbearing potential (FOCBP) must have a negative serum or urine pregnancy test (minimum sensitivity 25 IU/L or equivalent units of HCG) within 24 hours prior to the start of study treatment.
- c) Females must not be breastfeeding.
- d) FOCBP must agree to follow instructions for method(s) of contraception ([Appendix 4](#)) for the duration of treatment with DCV+SOF plus 5 half-lives of study treatment plus 30 days (duration of ovulatory cycle) for a total of 5 weeks post-treatment completion.
- e) Males who are sexually active with FOCBP must agree to follow instructions for method(s) of contraception ([Appendix 4](#)) for the duration of treatment with DCV+SOF plus 5 half-lives of the study treatment plus 90 days (duration of sperm turnover) for a total of 14 weeks post-treatment completion. In addition, male participants must be willing to refrain from sperm donation during this time.
- f) Azoospermic males are exempt from contraceptive requirements. FOCBP who are continuously not heterosexually active are also exempt from contraceptive requirements, and still must undergo pregnancy testing as described in this section.

Investigators shall counsel FOCBP, and male participants who are sexually active with FOCBP, on the importance of pregnancy prevention and the implications of an unexpected pregnancy. Investigators shall advise on the use of highly effective methods of contraception, which have a failure rate of < 1% when used consistently and correctly ([Appendix 4](#)).

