6.4.1 Retesting During Screening or Lead-In Period

This study permits the re-enrollment of a participant that has discontinued the study as a pre-treatment failure (ie, participant has not been treated). If re-enrolled, the participant must be re-consented.

Retesting of laboratory parameters and/or other assessments within any single Screening period will be permitted (in addition to any parameters that require a confirmatory value).

The most current result prior to dosing is the value by which study inclusion will be assessed, as it represents the participant's most current clinical state.

Laboratory parameters and/or assessments that are included in [Table 2-1](#), Screening Procedural Outline, may be repeated in an effort to find all possible well-qualified participants. Consultation with the Medical Monitor may be needed to identify whether repeat testing of any particular parameter is clinically relevant.

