2.2 Treatment Assignment

All participants receive DCV+SOF in Cohort 1 (12 to < 18 years), Cohort 2 (6 to < 12 years), and 3 (3 to < 6 years). Cohorts are determined by age at Day 1 assigned by Interactive Response Technology (IRT), not age at enrollment collected on the Case Report Form (CRF).

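### Three eligibility-deviation rules in SAP Appendix 1 contradict the protocol and can leave an ineligible treated participant out of a descriptive table (low impact)

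*SAP*

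**What the plan says.** **Repeat values.** Protocol 6.4.1 allows screening assessments to be repeated within a screening period and says which value decides: "The most current result prior to dosing is the value by which study inclusion will be assessed". SAP Appendix 1 (Eligibility Deviations) uses another rule. A participant with several pre-treatment values is "considered to have an eligibility deviation only if all pre-treatment measurements meet the deviation criterion".

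**Age.** Inclusion criterion 3a in Protocol 6.1 admits participants "3 to < 18 years of age on Day 1 of study treatment". The SAP check reads "Inclusion criterion 3a: Age < 3 or > 18 years at enrollment". SAP 2.2 uses the protocol's reference date for another purpose: "Cohorts are determined by age at Day 1 assigned by Interactive Response Technology (IRT), not age at enrollment".

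**ALT/AST.** Exclusion criterion 3b in Protocol 6.2 excludes values at or above 10 x ULN. The SAP check flags only values above 10 x ULN.

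**Use.** Under SAP 6.2 and Appendix 1 these deviations are summarised as counts in treated participants. SAP 6.2 reserves the summary for programmable deviations that might bear on how the results are interpreted.

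**The concern.** A reader takes an empty row in a deviation table to mean that every treated participant met that criterion. This is safe only if the program applies the protocol's own rule. Here the repeat-value and ALT/AST rules are more lenient than the protocol, so their errors all go towards under-reporting. The age check uses a different limit and a different date, so it can err both ways. What is at stake is the accuracy of a count of ineligible participants, not an estimate of exposure, response or safety.

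**Working it through.** The plan gives no figure to reproduce. The check is to apply each SAP rule and the matching protocol rule to the same cases.

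**(a) Repeat values.** Write P for a pass and F for a fail, in time order. The protocol makes a participant ineligible if the last value is F. The SAP flags only if every value is F. For k values, 2^(k-1) sequences end in F, the SAP flags 1 of them, and 2^(k-1) - 1 are missed.

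| k | Ineligible by protocol | Flagged by SAP | Missed |
|---|---|---|---|
| 1 | 1 | 1 | 0 |
| 2 | 2 | 1 | 1 (PF) |
| 3 | 4 | 1 | 3 (PPF, PFF, FPF) |

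These are counts of logical cases, not probabilities. If all values fail, the last one fails, so the SAP rule never flags an eligible participant. Fail-then-pass is cleared under both rules.

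Which values count is itself unclear. Appendix 1 ends the screening portion before Day 1, but its repeat-value rule speaks of all pre-treatment measurements. SAP 5.1 classes Day 1 laboratory and virology values as pre-treatment, and Protocol Table 2-2 schedules both on Day 1. If only screening values count, disagreement needs a retest. If Day 1 values count too, the scheduled samples alone supply two values.

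**(b) Age.** Inputs: the 42-day screening period (Protocol 5.1), or 42/365.25 = 0.115 years. Protocol: ineligible if Day 1 age is < 3 or >= 18. SAP: flagged if enrolment age is < 3 or > 18.

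| Enrolment age | Gap | Day 1 age | Protocol | SAP | Result |
|---|---|---|---|---|---|
| 17.95 | 42 days | 17.95 + 0.115 = 18.065 | ineligible | not flagged | missed |
| 18.0 | 0 | 18.0 | ineligible | not flagged | missed |
| 18.5 | 0 | 18.5 | ineligible | depends on storage | see below |
| 19.0 | 0 | 19.0 | ineligible | flagged | agree |
| 2.95 | 42 days | 2.95 + 0.115 = 3.065 | eligible | flagged | false flag |
| 3.0 | 0 | 3.0 | eligible | not flagged | agree |

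The documents do not say whether enrolment age is held in decimal or completed years. In decimal years 18.5 is flagged. In completed years it is held as 18, which is not above 18, so it is missed.

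**(c) ALT/AST.** At 9.99 x ULN neither rule acts, and at 10.01 x ULN both do. At exactly 10 x ULN the protocol excludes and the SAP does not flag. The rules differ at that value only.

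With the protocol's rules in place of the SAP's, every missed case above is flagged and the false age flag disappears.

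**The case against.** The strongest reply is that nothing of consequence depends on these checks. The table is descriptive. None of the populations in SAP 5.3 removes anyone for a deviation. The early-termination note in Protocol 10.3 limits reporting to PK, SVR and select safety data, with no statistical analyses, so the table may never be produced. All of this stands and sets the severity.

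On age, Protocol 5.1 reports that only participants aged 12 to under 18 were enrolled, and no cohort includes age 18. SAP 6.3.2.1 tabulates both Day 1 and enrolment age, and the age-group summary in SAP 6.3.1.1 has an adult row starting at 18. An 18-year-old would be visible elsewhere. Likewise, SAP 6.6.4 provides listings of the main laboratory tests. This also stands, but it makes an error in the check recoverable and does not make the check right.

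On repeats, a missed case needs a pass, then a fail, then dosing anyway. Protocol 6.4.1 says assessments "may be repeated in an effort to find all possible well-qualified participants", which suggests that fail-then-pass is the usual order, and there the rules agree. That is a fair point about frequency, which the documents do not let us estimate.

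It can also be said that SAP 6.2 covers only certain programmable criteria and is no full register of ineligibility. That governs which criteria are chosen, not how a chosen criterion is tested.

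A further objection concerns the remedy. A program that simply takes the last pre-dose sample could use a Day 1 laboratory result that the investigator did not have at dosing, and so create false deviations. This is right, and the fix has to guard against it.

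**Conclusion.** The point holds as a contradiction between the current SAP and the current protocol on three rules. Each can leave a protocol-ineligible treated participant out of the deviation table, and the age rule can also flag an eligible child. The false flag is moot in this trial because no Cohort 3 participants were enrolled. The impact is low: participants shown to be affected number 0 of 5, and no population, endpoint or sample size changes.

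A reader might infer two stronger things. The first is that ineligible participants were treated, or that results are biased. The documents give no individual values that show this, and they report all five as 12 to under 18 years. The second is that the SAP's weight check, which lacks the Cohort 1 lower limit of 45 kg, hides deviations. The summary of changes lists that limit as an addition in Revised Protocol 01. That revision reports every participant as already at least 41 weeks past treatment on 18 October 2019. The documents therefore do not establish a missed weight deviation.

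The conclusion rests on reading the protocol's most current result as one known before dosing. How enrolment age is stored changes how many ages check 3a could miss, but not that it differs from the protocol.

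**What to change.** In SAP Appendix 1:

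- **Repeat values.** Replace the all-values rule. Assess each repeatable criterion on the most current result available to the investigator before dosing, within the period the protocol sets for that criterion. Keep the confirmation rule for HbA1c. State that Day 1 samples reported after dosing do not count, so that they neither create nor cancel a deviation.
- **Check 3a.** Use Day 1 age from IRT, and flag < 3 or >= 18 years.
- **Check 3b.** Flag ALT or AST >= 10 x ULN.

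The cost is three wording edits and the matching program changes. Day 1 IRT age is already a planned demographic variable and the laboratory values are already collected, so no new data are needed. The repeat-value rule needs the date on which a result became available. If that date is not in the database, the SAP should say how Day 1 samples are handled, for example by leaving them out. The number of deviations could rise only if a participant's last available pre-dose value failed after an earlier pass, Day 1 age was 18, or ALT or AST was exactly 10 x ULN.
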